**TABLE 3: General Recommendations for Dermatologic Prophylaxis while receiving Panitumumab**

Personal hygiene	
 
Use of gentle soaps and shampoos for the body, e.g. pH5 neutral bath and shower formulations and tepid water.
 
Use of very mild shampoos for hair wash.
 
Only clean and smooth towels are recommended because of potential risk of infection. The skin should be patted dry after a shower, whereas rubbing the skin dry should be avoided.
 
Fine cotton clothes should be worn instead of synthetic material.
 
Shaving has to be done very carefully.
 
Manicure, i.e. cutting of nails, should be done straight across until the nails no longer extend over the fingers or toes. Cuticles are not allowed to be trimmed because this procedure increases the risk of nail bed infections
 

Sun protection	
 
Sunscreen should be applied daily to exposed skin areas regardless of season. Hypoallergenic sunscreen with a high SPF (at least SPF30, PABA free, UVA/UVB protection), preferably broad spectrum containing zinc oxide or titanium dioxide are recommended
 
Patients should be encouraged to consequently stay out of the sun.
 
Protective clothing for sun protection and wearing a hat should be recommended.
 

Moisturizer treatment	
 
It is important to moisturize the skin as soon as anti-EGFR therapy is started.
 
Hypoallergenic moisturizing creams, ointments and emollients should be used once daily to smooth the skin and to prevent and alleviate skin dryness.
 
Note: avoid greasy creams (e.g. petrolatum, soft paraffin, mineral oil based) and topical acne medications
 

Prevention of paronychia	
 
Patients should keep their hands dry and out of water if ever possible.
 
They should avoid friction and pressure on the nail fold as well as picking or manipulating the nail.
 
Topical application of petrolatum is recommended around the nails due to its lubricant and smoothing effect on the skin.
 

Patients may receive antibiotics (minocycline, doxycycline or trimethoprim/sulfamthoxazole) per institutional guidelines as preventives of skin toxicity.

Patients should be advised to avoid any foods known to aggravate diarrhea.

Prior to initiation of irinotecan, patients should be informed that they may experience diarrhea, and consideration should be given to providing patients prophylactic anti-diarrheal medication.

**A possible example of a prophylactic loperamide regimen against irinotecan-related diarrhea is the following:**

- Loperamide 4mg with the first dose of irinotecan, followed by 2mg every 4 hours for the first 3 days.
- After the first 3 days, take loperamide 2mg every 6-8 hours until the end of the first cycle of therapy whether the patient is experiencing diarrhea or not.

- Beyond the first cycle it may be continued at the discretion of the treating physician.
- Loperamide should be held if constipation develops.

## 9.2. Prohibited and/or Restricted Medications and Therapies

Other than CB-839, panitumumab and irinotecan, additional use of therapeutic anti-cancer treatment and/or standard chemo-, immunotherapy, hormone treatment (with the exception of megestrol acetate and use of anti-androgens and/or gonadorelin analogues for treatment of prostate cancer), or radiotherapy (other than palliative radiotherapy for symptom control) is not allowed concomitantly with the administration of study treatment.

Except for erythropoietin or darbepoetin alpha (Aranesp®), use of growth factors (i.e., G-CSF, GM-CSF, etc.) is not permitted in the first treatment cycle unless the patient experiences a hematologic DLT.

**Concomitant use of proton pump inhibitors (PPIs) should be avoided, if at all possible, due to significantly reduced exposure to CB-839.** (CB-839 is a weak base and, therefore, requires low pH conditions for optimal solubilization.) If PPI therapy is required, Investigators must discuss the strategy to dosing in combination with PPIs.

Antagonists of the H2 histamine receptor (e.g., ranitidine, famotidine, etc.) may be substituted for PPIs.

For patients unable to discontinue PPI therapy, or in cases that require restarting PPI therapy while on study, administration of CB-839 with an acidic beverage (e.g., orange juice) or supplement (e.g., citric acid) may be an option. If an acidic beverage/supplement is approved by the sponsor-investigator to be administered along with the CB-839 dose, it should be recorded on the appropriate eCRF, including the identity of the beverage/supplement, dosage, route, and start and stop dates of administration.

**CB-839 is a moderate inhibitor of CYP2C9**, therefore concomitant medications that are metabolized by CYP2C9 should either be given with caution (including closely monitoring for signs of toxicity or altered efficacy) or substituted for a non-CYP2C9 substrate.

Although CB-839 is not expected to inhibit CYP2C9 at the exposure levels planned, **caution is warranted when administering CB-839 to patients taking drugs that are highly dependent on CYP2C9 for metabolism and have a narrow therapeutic index.** A list of medications that are CYP2C9 substrates is provided below:

### **CYP2C9 Substrates with a narrow therapeutic index\***

- S-Warfarin (anticoagulant)
- Phenytoin (antiepileptic)

\*Narrow therapeutic index is defined as “CYP substrates with narrow therapeutic range refers to drugs whose exposure-response relationship indicates that small increases in their exposure levels by the concomitant use of CYP inhibitors may lead to serious safety concerns (e.g., Torsades de Pointes).”

<http://www.fda.gov/drugs/developmentapprovalprocess/developmentresources/druginteractions/abeling/ucm093664.htm>

### **Other CYP2C9 Substrates**

- NSAIDs (analgesic, antipyretic, anti-inflammatory)

- celecoxib
- lornoxicam
- diclofenac
- ibuprofen
- naproxen
- ketoprofen
- piroxicam
- meloxicam
- suprofen
- fluvastatin (statin)
- sulfonylureas (antidiabetic)
  - glipizide
  - glibenclamide
  - glimepiride
  - tolbutamide
  - glyburide
- irbesartan/losartan
- sildenafil (in erectile dysfunction)
- terbinafine (antifungal)
- amitriptyline (tricyclic antidepressant)
- fluoxetine (SSRI antidepressant)
- nateglinide (antidiabetic)
- rosiglitazone (antidiabetic)
- tamoxifen (SERM)
- torasemide (loop diuretic) ketamine

Exposure to irinotecan or its active metabolite SN-38 is substantially reduced in adult and pediatric patients concomitantly receiving the CYP3A4 enzyme-inducing anticonvulsants phenytoin, phenobarbital, carbamazepine, or St. John's wort. The appropriate starting dose for patients taking these or other strong inducers such as rifampin and rifabutin has not been defined.

Consider substituting non-enzyme inducing therapies at least 2 weeks prior to initiation of CAMPTOSAR therapy. **Do not administer strong CYP3A4 inducers with irinotecan unless there are no therapeutic alternatives.**

Irinotecan and its active metabolite, SN-38, are metabolized via the human cytochrome P450 3A4 isoenzyme (CYP3A4) and uridine diphosphate-glucuronosyl transferase 1A1 (UGT1A1), respectively. Patients receiving concomitant ketoconazole, a CYP3A4 and UGT1A1 inhibitor, have increased exposure to irinotecan hydrochloride and its active metabolite SN-38.

Co-administration of irinotecan with other inhibitors of CYP3A4 (e.g., clarithromycin, indinavir, itraconazole, lopinavir, nefazodone, nelfinavir, ritonavir, saquinavir, telaprevir, voriconazole) or UGT1A1 (e.g., atazanavir, gemfibrozil, indinavir) may increase systemic exposure to irinotecan or SN-38.

**Discontinue strong CYP3A4 inhibitors at least 1 week prior to starting irinotecan therapy.**

**Do not administer strong CYP3A4 or UGT1A1 inhibitors with irinotecan unless there are no therapeutic alternatives.**

### **9.3. Hematopoietic Growth Factors and Transfusional Support**

- Packed red blood cell and platelet transfusions should be administered only if clinically indicated, and should be avoided during the first 28 days after initiation of protocol-indicated treatment.
- Patients who enter the study on stable doses of granulocyte colony-stimulating factor, granulocyte-macrophage colony stimulating factor, erythropoietin, or darbepoietin may continue such treatment (provided such treatment was initiated at least 14 days prior to starting study treatment), and patients may start such treatment drug during the study (at the discretion of the treating physician if clinically indicated) after the first 28 days of following initiation of protocol-indicated treatment.

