- Treatment failure not meeting the criteria for PD, but considered by the investigator to require treatment discontinuation (e.g. clinical progression)
- Requirement for a significant surgical procedure

Note: Patients requiring a minor surgical procedure (e.g. port placement, skin abscess drainage) may continue at the investigator's discretion following discussion with the sponsor-investigator or designee. A brief interruption in therapy may be considered.

- An intercurrent illness which, in the opinion of the investigator, would prevent completion of trial-related evaluations
- The investigator judges it necessary due to medical reasons (e.g. significant deterioration in performance status)
- Required use of a prohibited concomitant medication, as defined in Section 9. Note: subject to discussion with and approval by the sponsor-investigator, inadvertent isolated receipt of a prohibited concomitant medication (e.g. incidental to acute management of an adverse event) does not require permanent discontinuation.
- The patient becomes pregnant during treatment  
(Cases of pregnancy that occur during maternal or paternal exposures to study treatment should be reported. Data on fetal outcome and breast-feeding may be collected for regulatory reporting and drug safety evaluation.)
- Significant deviation from the protocol or eligibility criteria. Such patients will be considered protocol violations and may be discontinued from treatment after discussion with the sponsor-investigator.
- Noncompliance with trial procedures may require discontinuation after discussion with the sponsor-investigator
- Termination of the trial by the sponsor-investigator

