  - A life-threatening bleeding event which results in urgent intervention and admission to an Intensive Care Unit
- Any Grade 5 hematologic or non-hematologic toxicity excluding death due to disease progression

3) **DLT for inability to initiate Cycle 2 within 4 weeks of scheduled treatment**

- Due to slow recovery from adverse event classified by the investigator as possibly, probably or definitely related to CB-839, or to the combination of CB-839 + panitumumab/irinotecan and failure to meet protocol-defined retreatment criteria.

Subjects who have experienced a DLT do not automatically require discontinuation of protocol-indicated treatment, unless the nature or severity of the DLT is also an adverse event that would require permanent discontinuation of study as elsewhere defined by the protocol. Rather, a patient who has experienced a DLT should be evaluated for consideration of an appropriate dose hold or dose modification which, if consistent with the protocol, would allow continued dosing under revised circumstance.

Dose reductions are not allowed during the DLT window for a patient to count in dose-escalation decisions. After Cycle 1, dose reductions or interruptions for adverse events may take place at any time as otherwise consistent with the protocol.

For purpose of ensuring appropriate opportunity to determine the maximum tolerated dose (MTD) of CB-839 in combination with panitumumab + irinotecan, a subject who is withdrawn from the study prior to

completing the DLT assessment window (i.e. first 28 days after initiating protocol-indicated therapy on Cycle 1, Day 1) for reasons other than a DLT will not be considered evaluable for DLT and will be replaced.

Additionally, if a patient discontinues study treatment for reasons clearly not related to study treatment (in the judgement of the investigator), after completing less than 75% of scheduled oral doses of CB-839 and/or less than 2 planned infusions of panitumumab and 2 planned infusions of irinotecan over the first 28 days after initiating protocol-indicated treatment on Cycle 1, Day 1, then that patient will be considered not evaluable for response to overall protocol-indicated treatment and may be replaced with a new patient.

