**TABLE 5: Reconciliation of AE Severity Grades in CTCAE v4.03 versus Figure 3**

CTCAE v4.03 severity grade a	Equivalent to	Figure 3 severity
Grade 0, 1 or 2	=	No / Mild / Moderate
Grade 3	=	Severe
Grade 4	=	Life Threatening or Disabling

(As needed for purpose of managing potential panitumumab-related adverse event.)

a NCI's Common Terminology Criteria for Adverse Events (NCI CTCAE), Version 4.03, dated June 14, 2010.

Dose delays and or modifications for panitumumab are to be considered for skin reactions of Grade 3 that are symptomatic; or which are considered intolerable at any grade.

**Exception for Grade 3 *asymptomatic* rash:** Note that rash of Grade 3 by body surface area (BSA) but which is asymptomatic does not require panitumumab treatment delay (or dose reduction) if uninterrupted panitumumab treatment is medically acceptable per investigator discretion.

Note: If, during the course of managing a patient's panitumumab treatment, conflicting guidance were to be detected between the management guidance as presented by narrative in Section 10.3, versus the algorithm presented in Figure 3, the investigator may elect either course of action deemed most appropriate by the investigator.

If panitumumab is held for toxicity, tolerated treatment with CB-839 + irinotecan may continue as scheduled. Alternatively, if panitumumab is delayed, the investigator may choose to also delay administration of irinotecan.

Delays of panitumumab administration beyond 6 weeks of last administered dose of panitumumab are not allowed. **Subjects who miss 3 or more consecutive scheduled doses of panitumumab due to toxicity or who are unable to receive a dose of panitumumab within 6 weeks of having received their previous dose of panitumumab due to toxicity will be considered unable to tolerate panitumumab and will not be retreated with panitumumab.** Additional consideration may be made toward continuing treatment with CB-839 + irinotecan alone.

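### Sections 9.2 and 9.3 conflict on continuing G-CSF/GM-CSF in Cycle 1; in Phase I, following 9.3 could hide a neutrophil-based DLT (minor).

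*Combined protocol and SAP*

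**What the plan says.** Section 9.2 states that "use of growth factors (i.e., G-CSF, GM-CSF, etc.) is not permitted in the first treatment cycle unless the patient experiences a hematologic DLT". The sentence opens with its one drug-based exemption: "Except for erythropoietin or darbepoetin alpha".

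Section 9.3 states: "Patients who enter the study on stable doses of granulocyte colony-stimulating factor, granulocyte-macrophage colony stimulating factor, erythropoietin, or darbepoietin may continue such treatment". The condition is a start at least 14 days before study treatment. On new starts of the same four agents it says "patients may start such treatment drug during the study (at the discretion of the treating physician if clinically indicated) after the first 28 days" of protocol treatment.

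Section 9.1 lets patients keep their current medication unless the protocol restricts it, and gives Section 9.2 as an example of such a restriction.

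Section 10.1 defines the DLT window as Cycle 1, the first 28 days after the first CB-839 dose. Hematologic DLTs include Grade 3 or higher febrile neutropenia and Grade 4 neutropenia lasting more than 5 days. An event counts only if the investigator relates it to CB-839 or to the combination. The section has a counting rule for dose changes, "Dose reductions are not allowed during the DLT window for a patient to count in dose-escalation decisions", but none for growth-factor support.

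**The concern.** For a patient who arrives on stable G-CSF or GM-CSF, one section forbids in Cycle 1 what the next permits. Cycle 1 is also the period in which Phase I toxicity is counted, and both neutrophil-based DLT criteria rest on the count that these drugs raise. Irinotecan is part of the Phase I triplet, and Sections 9.1 and 12.3 list neutropenia among its common reactions.

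The handling of the patient depends on which section is followed. Under 9.2, a patient who needs G-CSF falls under a listed reason for stopping treatment, "Required use of a prohibited concomitant medication, as defined in Section 9" (inadvertent isolated use can be excused). A patient withdrawn before Day 28 "for reasons other than a DLT will not be considered evaluable for DLT and will be replaced". Under 9.3 the patient stays on treatment and is counted. If the patient's only DLT would have been a neutrophil event attributed to CB-839 or the combination, and the support suppressed it, the CRM receives a non-DLT where a DLT belonged. The dose carried into Phase II rests on at most 12 such outcomes.

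**Working it through.** **1. The two rules for Cycle 1, side by side**

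| Situation | Section 9.2 | Section 9.3 |
|---|---|---|
| Stable G-CSF/GM-CSF, started at least 14 days before | Barred | Permitted |
| New G-CSF/GM-CSF after a hematologic DLT | Permitted | Mentions starts after 28 days; silent on this case |
| New erythropoietin/darbepoetin | Exempt from the bar | Mentions starts after 28 days |

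Only the first row sets an express bar against an express permission.

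**2. Search for text that settles row 1.** Section 9.2 speaks of use, not of starting, and stable G-CSF is not among its exceptions. Section 4.1 requires ANC of at least 1,500/µL but not without support, and Section 4.2 does not exclude growth-factor use. Section 9.1 points towards 9.2 without ranking it above 9.3. Section 10.3.3 has a tie-break for a different conflict (panitumumab narrative against figure), where "the investigator may elect either course of action deemed most appropriate by the investigator"; it does not reach this one.

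**3. Sensitivity of the CRM to one missed DLT.** Inputs from Section 15: Pr(tox at level i) = p_i^exp(α), p = 0.1/0.2/0.3 for levels -1/1/2, α ~ N(0,2), target 0.30, cohorts of 3, at most 12 patients, no skipping, stop if Pr(rate at level -1 > 0.3) > 0.9. The start at level 1 is from Section 8.2. My readings: 2 is a variance, the posterior mean of α is plugged in, and all outcomes of four cohorts are enumerated exactly.

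The plan's own figures first, for final selection of level 2 in scenarios 1-4:
- Plan: 0.63, 0.79, 0.48, 0.33.
- Enumeration: 0.640, 0.791, 0.482, 0.336.

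The match does not extend to every cell. In scenario 4 the enumeration gives level 1 = 0.346 (plan 0.43) and Stop = 0.053 (plan 0.01). What follows is therefore an illustration.

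Estimated rates at levels -1/1/2 after cohort 1 at level 1:
- 0/3: 0.002/0.013/0.039, so escalate.
- 1/3: 0.224/0.351/0.457, so stay. If 2 is read as an SD: 0.249/0.379/0.484, so de-escalate.

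One masked DLT thus turns a stay or de-escalate decision into an escalation. Later data can reverse it: 0/3 at level 1 followed by 2/3 at level 2 gives 0.164/0.282/0.388, so back to level 1.

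**4. Size for one supported patient.** Assumptions not in the plan: one such patient in cohort 1, and a share m of that patient's DLT risk that is neutrophil-based, attributable and fully masked. In scenario 4 (true rates 0.2/0.3/0.4), the chance of 0/3 in cohort 1 is 0.7² × [1 − 0.3(1 − m)]:
- m = 0: 0.49 × 0.70 = 0.343
- m = 0.10: 0.49 × 0.73 = 0.358
- m = 0.25: 0.49 × 0.775 = 0.380
- m = 0.50: 0.49 × 0.85 = 0.417

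Final selection of level 2:

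| Scenario | m = 0 | 10% | 25% | 50% |
|---|---|---|---|---|
| 1 | 64.0% | 64.5% | 65.3% | 66.5% |
| 2 | 79.1% | 79.4% | 79.9% | 80.7% |
| 3 | 48.2% | 48.8% | 49.7% | 51.3% |
| 4 | 33.6% | 34.3% | 35.3% | 36.9% |

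In scenarios 1 and 2 the true rate at level 2 is 0.30 or less, so the shift does no harm. In scenario 3 levels 1 and 2 (0.25 and 0.35) are equally far from 0.30. Only scenario 4 moves towards an over-target dose, by 34.3 − 33.6 = 0.7 to 36.9 − 33.6 = 3.3 points. With 2 read as an SD, scenario 4 goes from 34.2% to 34.8/35.8/37.4%.

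**The case against.** The affected group may be empty. A Phase I patient would have to be on stable G-CSF/GM-CSF for at least 14 days although Section 4.2 requires 28 days without anti-cancer treatment. Neutropenia is not among the CB-839 reactions in Section 12.2, and neutropenia attributed to irinotecan alone is not a DLT. A careful reader can also take 9.3 as a specific exception to 9.2, or take the pointer in 9.1 as a sign that 9.2 governs. The first two points stand and keep the matter minor. The last does not remove the conflict, because the two readings lead to opposite answers and no text chooses between them.

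Four stronger readings are tempting and are not supported:
- **That the sections contradict each other on new starts as well.** Rows 2 and 3 of the table can be read so, but 9.3 is worded permissively and does not say that starts are allowed only after 28 days. The difference is an inference.
- **That any supported patient is counted as a non-DLT.** Every other DLT still counts. The error needs a sole DLT that was neutrophil-based, attributable and masked.
- **That the dose decision is badly exposed.** If 10% or 20% of all DLTs in the trial were masked, scenario 4 selection of level 2 would rise from 34% to 43% or 53%. That presumes support throughout the trial, which nothing in the plan suggests.
- **That Phase II is compromised.** DLT surveillance is for dose escalation only (Section 7.6), Phase II has no irinotecan, and no DLT-based dose decision is made there.

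**Conclusion.** The conflict on continuing stable G-CSF/GM-CSF in Cycle 1 is real and on the page. It matters in Phase I because Cycle 1 is the DLT window. It is minor. At most 12 patients could be exposed and few if any are likely to be. Under the stated assumptions the only harmful shift is 0.7 to 3.3 percentage points in scenario 4, which later cohorts can partly correct. That range rests on assumed masking shares and on a model reading that reproduces the plan's level 2 column but not its whole table. The textual finding does not depend on it.

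**What to change.** Amend Section 9.3 so that in Phase I G-CSF/GM-CSF may be neither continued nor started during Cycle 1 except after a hematologic DLT, as 9.2 states, and so that erythropoietin and darbepoetin follow the 9.2 exemption. This also removes the doubt about new starts in Phase I. The cost is one sentence, and an occasional patient who needs continuing G-CSF/GM-CSF is delayed or not enrolled.

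Two further changes are not recommended:
- **A rule in 10.1 replacing supported patients who have no DLT.** It would bias the DLT rate upward. In scenario 4 the chance that the slot yields a DLT becomes q + (1 − q) × 0.30 with q = 0.30(1 − m), that is 0.489, 0.457 and 0.405 for m = 10, 25 and 50%. Selection of level 2 falls from 33.6% to 29.5, 30.2 and 31.3%, a shift of −4.1 to −2.3 points against +0.7 to +3.3 for masking. That trade is debatable at best.
- **A Phase II restriction in 9.3.** The difference in wording would remain there, but it touches supportive care only.

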### **9.4. Palliative Radiotherapy**

Radiotherapy other than palliative radiotherapy for symptom control is not allowed concomitantly with the administration of protocol-indicated treatment.

After study enrollment, palliative radiotherapy may be given for bone pain or for other reasons, provided that the total dose delivered is in a palliative range according to institutional standards.

The irradiated area cannot be used for tumor response assessment.

During palliative radiotherapy, study treatment should be delayed and may be resumed once the patient has recovered from any radiation associated toxicity.

If a treatment cycle is interrupted for more than 28 days, the decision to continue will be made by the investigator in agreement with the sponsor-investigator. Continuous interruption of >28 days due to palliative radiotherapy will not be allowed.

